3.5.3 Outcome	
3.5.4 Cases	11
3.5.5 Controls	12
3.5.6 Exposure (vaccination)	13
3.5.7 Risk groups	13
3.5.8 Confounding factors/effect modifiers	14
3.5.8 Sample size	15
3.5.10 Data	16
3.5.11 Analysis	17
4 Limitations	18
4.1 Sample size	18
4.2 Negative confounding	18
4.3 Positive confounding	18
4.4 Misclassification bias	18
4.5 Inclusion of persons with A(H1N1)v infection prior to the outbreak	18
4.6 Overestimation of IVE	18
5 Consent	
6 Dissemination of results	19
7 Logistical aspects	19
8 Budget	
References	20
Annex: List of variables, definitions and coding	21

Abbreviations

EEA European Economic Area

EU European Union

GP General practitioner

ILI Influenza-like illness

IVE Influenza vaccine effectiveness

OR Odds ratio
RR Relative risk

VE Vaccine effectiveness

(Tick/check mark indicates specific action to be taken by Member States or additional information to be added in the format of annexes to current protocol.)

1 Background

With the recent emergence of the A(H1N1)v virus and its continued spread worldwide, at least four new vaccines against influenza A(H1N1)v have been developed and three have been already approved in the European Union (EU). Once available, it is crucial to rapidly estimate the vaccine effectiveness of the new vaccines against pandemic influenza. In addition, studies are needed to determine if the seasonal flu vaccination is protective against the new virus.

Having early influenza vaccine effectiveness (VE) estimates at European level as soon as possible after the pandemic vaccine is available and monitoring it along the course of the epidemic/pandemic is essential to:

- decide on recommendations for the use of the vaccine;
- target complementary or alternative public health measures (e.g. antivirals) for population subgroups in which vaccine is less effective;
- allow more precise estimates of the impact of current vaccination strategies on the burden of disease to support vaccination campaigns;
- trigger further investigations on pandemic vaccines (improve composition, use of adjuvants, need for booster doses);
- better manage and respond to expected reports of vaccine failures; and
- counterbalance the reports of adverse events following immunisation by providing elements for an adequate risk management and cost-effectiveness analysis.

In the current European context, only observational studies can be used to obtain real-time influenza VE estimates.

During the influenza 2008–09 season, the European Centre for Disease Prevention and Control (ECDC) funded five pilot case-control studies (Portugal, Spain, Denmark, Romania, Hungary) and two pilot cohort studies (Navarra (Spain) and UK) under the coordination of EpiConcept to measure seasonal influenza vaccine effectiveness (IVE) in the elderly (\geq 60 or \geq 65 years old). The pilot studies were based on general practitioner (GP) surveillance networks and included a set of variables to adjust for positive and negative confounding.

These and additional case-control and cohort studies will continue to measure seasonal and pandemic IVE in the 2009–10 season, with ECDC funding and EpiConcept coordination. Screening method studies will also be included.

In addition to measuring IVE through these larger studies, IVE can also be estimated through investigation of clusters of influenza. Through analysis of influenza clusters, rapid IVE estimates potentially early in the season can be obtained. An advantage of cluster analysis is that in some settings (e.g. schools, care homes) vaccination records might be easily obtainable. Investigation can take place at the same time that control measures are being carried out.

We present here a core European protocol describing methods for investigation of clusters to measure IVE. The protocol will be updated as more information on pandemic vaccine and pandemic influenza become available. It is intended to be used by teams from national or local public health institutions that have to investigate a cluster of influenza. The specifics of each investigation will vary according to the context and can be detailed in annexes. Given the main study designs in cluster investigation situations, we have divided the methods section into two: cohort study and case-control study.

2 Objectives

2.1 Primary objective

To measure the effectiveness of pandemic vaccines against A(H1N1)v laboratory-confirmed influenza in EU/EEA countries.

2.2 Secondary objectives

If sample size allows, vaccine effectiveness can be obtained for the following strata:

- to provide VE estimates of seasonal vaccine against A(H1N1)v
- to estimate VE by age group;
- to estimate VE by risk group;
- to measure VE by vaccine brand;
- to estimate VE against other outcomes, such as hospitalisation, pneumonia, death.
- ☑ Other outcomes to be detailed in study-specific annexes.
- ☐ The specific secondary objectives of each investigation should be detailed in study-specific annexes.

3 Methods

3.1 Definition of cluster

A cluster is defined as a group of cases of pandemic influenza (H1N1) 2009 that are related in time and space. Examples include cases in residential care homes, schools, universities, out-of-home childcare settings, healthcare, workplace and household clusters, mass gathering events and outbreaks in cruise ships. Identification of a cluster suitable for measuring vaccine effectiveness – adapted from Orenstein et al¹:

- absence of substantial prior influenza (H1N1) activity in the studied group;
- population containing both vaccinees and non-vaccinees;
- adequate population size in the group to be studied;
- high overall attack rate;
- good vaccination records available to differentiate non-vaccinees from vaccinees.

In addition, the cluster has to be identified early enough to obtain samples within a short delay between onset of symptoms and swabbing (to reduce misclassification of outcome), if laboratory-confirmed outcomes are used.

3.2 Preliminary steps

For all study designs, preliminary steps for the cluster investigation are the following:

- Confirm the cluster/outbreak.
- Verify the diagnosis of A(H1N1)v infection.
- Case identification: all persons with respiratory symptoms should be identified within the cluster (retrospectively and prospectively, if appropriate). Swabs should be taken as soon as possible. For information on case definitions and laboratory methods, see the respective study design chapters. In a well-defined cluster, the entire population can be surveyed.
- Establishing a case line listing with basic information on the cases or a line listing the total population, if the cluster is small.
- Cases should be described in terms of time, place and person.
- A study design approach for an analytical study should be decided upon (see next section).

3.3 Study design

Where the study population within a cluster is well defined (e.g. all residents of a nursing home, all pupils of a school, all passengers of a cruise ship), a cohort study could be the study design of choice. Otherwise, a case-control (traditional, case-cohort or density case-control study design) could be considered. The protocol contains a methods section for each of these study designs.

The study design should be detailed in study-specific annexes and the irrelevant study design sections in 'Methods' can be deleted.

3.4 Cohort study design

Delete section if not applicable

3.4.1 Study population

The study population is defined as the population at risk of A(H1N1)v infection within the population in which the cluster occurs.

3.4.2 Study participants

If the cluster has a manageable population size, the whole study population will be eligible for the VE study. If the population is very large and the attack rate is high, then a systematic or random sample of this population should be selected for the study.

A sample size calculation should be detailed in study-specific annexes.

¹ Orenstein WA, Bernier RH, Dondero TJ, Hinman AR, Marks JS, Bart KJ, et al. Field evaluation of vaccine efficacy. Bull World Health Organ 1985;63(6):1055-68.

Exclusion criteria

Study participants are excluded if they are not eligible for vaccination with the pandemic/seasonal vaccine because of having a condition listed in the summary of products characteristics (e.g. anaphylactic hypersensitivity to eggs or its components), or if they refuse participation. People with laboratory-confirmed diagnosis of A(H1N1)v infection since the beginning of the pandemic (or other date according to the duration of the pandemic) and prior to the beginning of the outbreak/cluster of influenza are excluded as they are not at risk.

People who were not swabbed but had respiratory symptoms in the interval from the beginning of the pandemic (or other date according to the duration of the pandemic) and prior to the beginning of the outbreak/cluster will be documented and analyses carried out including and excluding them.

Reasons for exclusion must be documented.

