3.4.7 Risk groups

Pandemic vaccine

According to ECDC interim guidance², the risk groups to be considered for the pandemic vaccine are:

- people aged less than 65 years with chronic underlying conditions, namely:
 - chronic respiratory diseases;
 - chronic cardiovascular diseases;
 - chronic metabolic disorders (notably diabetes);
 - chronic renal and hepatic diseases;

http://www.ecdc.europa.eu/en/publications/Publications/Forms/ECDC_DispForm.aspx?ID=388

² European Centre for Disease Prevention and Control (ECDC). Interim guidance: Use of specific pandemic influenza vaccines during the H1N1 2009 pandemic. Stockholm: ECDC; 2009. Available from:

- persons with deficient immunity (congenital or acquired);
- chronic neurological or neuromuscular conditions;
- any other condition that impairs a person's immunity or prejudices their respiratory function;
- young children (especially under the age of two years);
- pregnant women.

Other target groups may include healthcare workers, essential service workers, caregivers of infants < 6 months old.

Seasonal vaccine

Individuals are considered to belong to a risk group if their patient record contains any of the ICD codes listed on Table 1 or if they report having one of the underlying conditions included in the same table..

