3.5.4 Cases

Case identification

Information on signs and symptoms of respiratory illness will be collected from all study participants and include:

- cough
- sore throat;
- shortness of breath;
- fever;
- myalgia;
- headache;
- malaise.

All persons presenting with any of those signs and symptoms since the beginning of the cluster should be swabbed.

Mode of specimen collection, storage and transport for each study should be listed in study annexes.

EU ILI definition

A case of ILI is defined as an individual presenting:

- sudden onset of symptoms AND at least one of the following four systemic symptoms:
 - fever or feverishness,
 - malaise,
 - headache,
 - myalgia,
- AND at least one of the following three respiratory symptoms:
 - cough,
 - sore throat,
 - shortness of breath.

Clinical criteria (from EU novel influenza virus A(H1N1) case definition (30/4/2009):

Any person with one of the following three:

- fever > 38°C AND signs and symptoms of acute respiratory infection,
- pneumonia (severe respiratory illness),
- death from an unexplained acute respiratory illness.

Laboratory confirmation

Influenza laboratory confirmation will be done using RT-PCR and/or culture.

☑ RT-PCR characteristics for each study should be listed in study annexes.

Isolates will undergo a molecular analysis for currently circulating influenza A viruses (subtypes H3 and H1) and influenza B. A systematic subset will undergo gene sequencing.

Selection of isolates for each study should be specified in study annexes.

If rapid diagnostic tests (RDTs) are to be used for laboratory confirmation, then their sensitivity and specificity needs to have been studied and documented in a similar situation (e.g. similar study population).

Case inclusion criteria

Cases are eligible if they meet the above case definition and accept to participate.

☑ Oral or written informed consent according to country procedures should be specified in study annexes.

Case exclusion criteria

Cases are excluded if they are not eligible for influenza vaccination because of having a condition listed in the summary of products characteristics (e.g. anaphylactic hypersensitivity to eggs or its components) or if they refuse participation. Reasons for exclusion will be documented.

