3.5.5 Controls

The selection of controls varies according to the nature of the cluster.

Controls must be representative of the source population from which the cases arise in respect to vaccination coverage. In a traditional case-control study, controls who are still disease free (i.e. who did not have A(H1N1)v infection or other outcome of interest) are chosen at the end of the cluster/outbreak. In a case-cohort study, controls are selected from persons who are disease-free at the beginning of the cluster/outbreak. Therefore, persons who got the outcome of interest during the cluster/outbreak can be included as controls. Control selection among people still free of the outcome of interest when a case arises forms a density case-control study.

Controls can be unmatched or matched to cases.

Selection and characteristics of controls should be listed in study annexes.

Control inclusion criteria

Controls are eligible if they meet the above control definition and accept to participate.

☑ Oral or written informed consent according to country procedures should be specified in the study annexes.

Control exclusion criteria

Controls are excluded if they are not eligible for influenza vaccination because of having a condition listed in the summary of products characteristics (e.g. anaphylactic hypersensitivity to eggs or its components) or if they refuse participation. People with laboratory-confirmed diagnosis of A(H1N1)v infection since the beginning of the pandemic (or other date, according to the duration of the pandemic) and prior to the beginning of the outbreak/cluster of influenza are excluded, as they are not at risk.

People who were not swabbed but had respiratory symptoms in the interval from the beginning of the pandemic (or other date, according to the duration of the pandemic) and prior to the beginning of the outbreak/cluster will be documented and analyses carried out including and excluding them.

Reasons for exclusion must be documented.

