vacc_05	Numeric (categorical)	0 = No 1 = Yes 8 = Don't know	Previous influenza vaccination 2005–6
vacc_04	Numeric (categorical)	0 = No 1 = Yes 8 = Don't know	Previous influenza vaccination 2004–5
Diabetes	Numeric (categorical)	0 = No 1 = Yes 8 = Don't know	Diabetes and endocrine
heart_dis	Numeric (categorical)	0 = No 1 = Yes 8 = Don't know	Heart disease
immune	Numeric (categorical)	0 = No 1 = Yes 8 = Don't know	Immunodeficiency and organ transplant
Lungdis	Numeric (categorical)	0 = No 1 = Yes 8 = Don't know	Lung disease
Severity	Numeric (count)	integer	Number of hospitalisations in the previous year for the chronic disease
fs_bath	Numeric (categorical)	0 = No 1 = Yes 8 = Don't know	Requires assistance to bath
Pregnant	Numeric (categorical)	0 = No 1 = Yes 8 = Don't know	Pregnancy status
Smoking		0 = Never 1 = Former 2 = Current 9 = Don't know	Never, former (stopped smoking at least one year before inclusion in the study), current smoker
Antivir	Numeric (categorical)	0 = No 1 = Yes 8 = Don't know	Recent use of antivirals
Antivirdate	Date	dd/mm/yyyy	Date of antiviral administration
Antivirdose	Text		Doses of antiviral taken
Antivirbrand	Text		Type of antiviral taken (brand name)
ili_prior	Numeric (categorical)	0 = No 1 = Yes 8 = Don't know	ILI since beginning of pandemic, but prior to cluster
Ili_prior_lab	Numeric (categorical)	0 = Negative 1 = Positive 2 = Not done 8 = Don't know	Laboratory result (positive/negative)
ili_prior_virus	Text		Laboratory result: virus type and subtype of recent ILI
contra	Numeric (categorical)	0 = No 1 = Yes 8 = Don't know	Exclusion criteria: contraindication for influenza vaccination

This table represents a selection of covariates. Variables can be included or excluded as necessary.

Other annexes containing details of specific studies should be added to the current protocol.

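### The ineligibility exclusion covers only a listed condition, so people who cannot be vaccinated because of age stay in as unvaccinated and, if their attack rate differs, can bias the crude VE and mixed age bands.

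*Protocol*

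**What the plan says.** The cohort exclusion in Protocol 3.4.2 removes people "not eligible for vaccination with the pandemic/seasonal vaccine because of having a condition listed in the summary of products characteristics", with egg hypersensitivity as the example. The case-control sections carry the same limit: "Cases are excluded if they are not eligible for influenza vaccination because of having a condition listed in the summary of products characteristics" (3.5.4) and "Controls are excluded if they are not eligible for influenza vaccination because of having a condition listed in the summary of products characteristics" (3.5.5). The matching Annex variable, contra, is defined as "Exclusion criteria: contraindication for influenza vaccination". None of these mentions age.

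The cohort population is set by risk of infection, not by the possibility of being vaccinated: "The study population is defined as the population at risk of A(H1N1)v infection within the population in which the cluster occurs" (3.4.1). The settings named in 3.1 include "out-of-home childcare settings, healthcare, workplace and household clusters". Section 3.1 asks for both vaccinees and non-vaccinees in the group as a whole, not within age bands.

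On age in the analysis:

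- Sections 3.4.11 and 3.5.11 stratify by age group without giving cut-points.
- The minimum confounder lists in 3.4.8 and 3.5.8 do not name age.
- The case-control model in 3.5.11 includes age as a preference; the cohort model in 3.4.11 is left to study annexes.
- The Annex collects date of birth and age.

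**The concern.** The exclusion rests on a sound principle: a person who could not have been vaccinated does not belong in a comparison of vaccinated with unvaccinated. The protocol applies it to one route of ineligibility, a medical condition, and leaves out the other, age.

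An age-ineligible person has no chance of exposure and so carries no information on VE. That person's illness still counts in the unvaccinated attack rate. If the age-ineligible have a higher attack rate than the other unvaccinated, crude VE is pushed up; if lower, it is pulled down. The same happens inside any age band that puts them together with people who could be vaccinated, which matters because VE by age group is a secondary objective (2.2).

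**Working it through.** **Plan's own figure.** Table 2 (3.4.9) gives power 0.76 for 200 exposed and 200 unexposed, attack rate 20% in the unexposed, risk ratio 0.5, alpha 0.05. With a pooled variance and a continuity correction, power = Φ((d − c − 1.96·se0)/se1):

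- d = 0.20 − 0.10 = 0.10
- c = ½(1/200 + 1/200) = 0.005
- se0 = √(2 × 0.15 × 0.85/200) = 0.0357
- se1 = √((0.2 × 0.8 + 0.1 × 0.9)/200) = 0.0354
- power = Φ(0.708) = 0.76, as printed (0.80 without the correction)

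This figure is not in dispute. It supplies the base case below.

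**Assumed inputs (not in the protocol).** True risk ratio 0.5, so VE 50%. Let f be the share of the unvaccinated who are age-ineligible, 5% to 20%. Let m be their attack rate relative to the other unvaccinated, 0.5 to 3.

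**Crude VE (cohort).** The unvaccinated attack rate is multiplied by (1 − f) + f·m, so

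crude VE = 1 − 0.5/((1 − f) + f·m)

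| f | m = 0.5 | m = 1 | m = 2 | m = 3 |
|---|---|---|---|---|
| 5% | 48.7% | 50.0% | 52.4% | 54.5% |
| 10% | 47.4% | 50.0% | 54.5% | 58.3% |
| 20% | 44.4% | 50.0% | 58.3% | 64.3% |

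For example, f = 20% and m = 3 gives 1 − 0.5/(0.8 + 0.6) = 0.643. The range is 44.4% to 64.3%, and the m = 1 column shows no bias at any share.

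**What age stratification does.** Take the 200/200 case with f = 20%: 40 age-ineligible and 160 other unvaccinated people, of whom 32 fall ill (20%); 20 of the 200 vaccinated fall ill (10%). Among the 40, 4 fall ill at m = 0.5 and 16 at m = 2.

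1. *Crude:* 1 − 0.10/(36/200) = 44.4% at m = 0.5; 1 − 0.10/(48/200) = 58.3% at m = 2.
2. *Age cut at the eligibility limit:* the ineligible stratum has no vaccinated people and zero Mantel-Haenszel weight. VE is 50.0% whatever m is.
3. *Coarse band:* put the 40 ineligible with 40 eligible unvaccinated (8 ill) and 40 vaccinated (4 ill). The rest are 160 vaccinated (16 ill) and 120 unvaccinated (24 ill).
   - Within the band: 1 − 0.10/(12/80) = 33.3% at m = 0.5; 1 − 0.10/(24/80) = 66.7% at m = 2.
   - Mantel-Haenszel, m = 0.5: numerator 4 × 80/120 + 16 × 120/280 = 9.524; denominator 12 × 40/120 + 24 × 160/280 = 17.714; VE = 46.2%.
   - Mantel-Haenszel, m = 2: the denominator becomes 24 × 40/120 + 13.714 = 21.714; VE = 56.1%.

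The coarse band takes away part of the overall bias, but the VE reported for the band itself is further from 50% than the crude figure.

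**Power after exclusion.** With 200 vaccinated and 160 unvaccinated, c = ½(1/200 + 1/160) = 0.0056, se0 = 0.0373, se1 = 0.0381, and power = Φ(0.559) = 0.71 (0.76 without the correction).

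The arithmetic is for the cohort risk ratio. No odds-ratio calculation was made for the case-control design, where the wording gap is the same.

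**The case against.** The strongest reply is that the protocol states no vaccination age limit. Its only hint is a possible target group, "caregivers of infants < 6 months old" (3.4.7), which does not say that the infants themselves cannot be vaccinated. The same section lists young children, especially those under two, as a risk group for the pandemic vaccine, so any ineligible band may be narrow. This stands: how often the problem arises, and how large it is, cannot be settled from the document.

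It is also fair to say that age is already handled: age groups come first among the stratification items in both designs, age is a baseline characteristic for which crude and adjusted estimates are compared, and the case-control model preferably includes it. This stands in part. Stratification removes the bias when a cut falls at the limit, but no cut-points are given. Cohort clusters may be small (4.1), and the case-control section aims for at least 80 cases and 80 controls per stratum (3.5.11); both favour wide bands. The crude VE has no such protection.

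A third reply is that this is a core template with annexes for local detail. An annex could carry the age limit, but nothing in the exclusion rules asks for one, and as worded they would leave age-ineligible people in.

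A reader might infer that VE in every childcare or household cluster is distorted, or that it is always overstated. The documents support neither. Bias needs age-ineligible people to be present and their attack rate to differ, and its direction depends on whether that rate is higher or lower. Nor is a cut exactly at the limit the only thing that helps: equal attack rates give no bias, and coarse bands give less.

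**Conclusion.** The gap in wording is real and is the same in 3.4.2, 3.5.4, 3.5.5 and the Annex. Reading a listed condition to include age would be strained, given the egg-hypersensitivity example and the contraindication flag. The consequence is conditional. With true VE 50%, f of 5–20% and m of 0.5–3, all assumed, crude VE lies between about 44% and 64%; the upper end needs both a 20% share and a threefold attack rate. The effect is nil where no such people are present or where m = 1, and the stratified estimate is free of it when an age cut matches the limit. The change is worth making because the template is meant for many clusters and the correction is small. Nothing here shows what the age limit is, or that any given cluster is affected.

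**What to change.** In 3.4.2, 3.5.4 and 3.5.5, extend the exclusion to people who cannot receive the vaccine under study because their age is outside the range for which it is authorised. Apply it separately for the pandemic and the seasonal vaccine, from date of birth, and count these people under the documented reasons for exclusion. Widen the Annex flag to match. The range should come from the product information for the vaccine in use; this review proposes none.

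The clause should not extend to age groups that are merely not offered vaccine. People in such groups may still be vaccinated, for example as members of a risk group or as healthcare workers (3.4.7), and excluding them would remove real vaccinees.

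For the stratified estimate, an age-stratum cut set at the same limit does the same job; the crude VE would still include the ineligible.

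Cost: wording only, since date of birth and age are already collected. The unvaccinated group becomes slightly smaller and nominal power falls, for example from 0.76 to about 0.71 if 40 of 200 unvaccinated leave. The people who leave carried no information on VE.
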